**Phase I/II Oncology liver chemistry increased monitoring criteria with continued therapy**

Liver Chemistry Increased Monitoring Criteria – Liver Monitoring Event	
Criteria	Actions

Subject with entry criteria ALT ≤ 2.5x ULN            ALT ≥ 3xULN but <5xULN and bilirubin <2xULN, without symptoms believed to be related to liver injury or hypersensitivity and who can be monitored weekly for 4 weeks
 
Subject with documented liver metastases/tumor infiltration at baseline AND entry criteria ALT > 2.5 x ULN but ≤ 5 x ULN            ALT ≥ 3x ULN and 1.5x baseline value but ALT <5x ULN and 2x baseline value and bilirubin <2xULN, without symptoms believed to be related to liver injury, or hypersensitivity and who can be monitored weekly for 4 weeks
	
 
Notify the GSK medical monitor within 24 hours of learning of the abnormality to discuss subject safety.
 
Subject can continue study treatment
 
Subject must return weekly for repeat liver chemistries (ALT, AST, alkaline phosphatase, bilirubin) until they resolve, stabilise or return to within baseline
 
If at any time subject meets the liver chemistry stopping criteria, proceed as described above
 
 
For subjects with entry criteria ALT ≤ 2.5 x ULN
 
 
If, after 4 weeks of monitoring, ALT <3xULN and bilirubin <2xULN, monitor subjects twice monthly until liver chemistries normalize or return to within baseline.
 
 
For subjects with documented liver metastases/tumor infiltration at baseline AND entry criteria ALT > 2.5 x ULN but ≤ 5 x ULN
 
 
If, after 4 weeks of monitoring, ALT <3xULN and <1.5x baseline value, and bilirubin <2xULN, monitor subjects twice monthly until liver chemistries normalize or return to within baseline
 

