#### Phase I/II liver chemistry stopping criteria and required follow up assessments

Liver Chemistry Stopping Criteria – Liver Stopping Event Subject with entry criteria ALT ≤ 2.5 x ULN	
ALT-absolute	ALT ≥ 5xULN
ALT Increase	ALT ≥ 3xULN persists for ≥4 weeks
Bilirubin	ALT ≥ 3xULN and bilirubin ≥ 2xULN (>35% direct bilirubin)
INR^2	ALT ≥ 3xULN and INR>1.5, if INR measured
Cannot Monitor	ALT ≥ 3xULN and cannot be monitored weekly for 4 weeks
Symptomatic	ALT ≥ 3xULN associated with symptoms (new or worsening) believed to be related to liver injury or hypersensitivity
Liver Chemistry Stopping Criteria – Liver Stopping Event Including subjects with documented liver metastases/tumor infiltration at baseline AND entry criteria ALT>2.5 x ULN but ≤5 x ULN	
ALT-absolute	Both ALT ≥ 5xULN and ≥2x baseline value
ALT Increase	Both ALT ≥ 3xULN and ≥ 1.5x baseline value that persists for ≥4 weeks
Bilirubin	ALT ≥ 3xULN and bilirubin ≥ 2xULN (>35% direct bilirubin)
INR^2	ALT ≥ 3xULN and INR>1.5, if INR measured
Cannot Monitor	Both ALT ≥ 3xULN and ≥ 1.5x baseline value that cannot be monitored for 4 weeks
Symptomatic	Both ALT ≥ 3xULN and ≥ 1.5x baseline value associated with symptoms (new or worsening) believed to be related to liver injury or hypersensitivity

Required Actions and Follow up Assessments following ANY Liver Stopping Event	
Actions	Follow Up Assessments

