LVEF	Ejection fraction below the institution's lower limit of normal (LLN)  AND  An asymptomatic, absolute decrease of >10% in LVEF compared to baseline	Withhold GSK2820151 and repeat evaluation of LVEF within 2 weeks  If LVEF recovers (defined as $\geq$ LLN and absolute decrease $\leq$ 10% compared to baseline) at any time during the next 4 weeks, after consultation and approval of the GSK medical monitor, the subject may be restarted on investigational drug(s) at a reduced dose. Monitoring to be performed at 2 and 4 weeks after restarting investigational drug(s) and then per protocol specifications.  If LVEF does not recover within 4 weeks, permanently discontinue investigational drug(s). Evaluation by a cardiologist will be conducted. Ejection fraction should continue to be monitored at 2 weeks, 4 weeks and every 4 weeks until 16 weeks or resolution, whichever is longer.
	Grade 3 or 4	Permanently discontinue GSK2820151. Evaluation by a cardiologist will be conducted. Ejection fraction should be monitored at 2 weeks, 4 weeks and then every 4 weeks until 16 weeks or resolution, whichever is longer.
Liver		Refer to procedures outlined in Appendix 3: Liver Safety Required Actions and Follow up Assessments
Hypo- and Hyperglycemia  Note: for management purposes, refer to mild, moderate and severe intensity criteria; however for CRF reporting use NCI-CTCAE version v4.03 Grade 1-5	Fasting blood glucose >150 mg/dL to 250 mg/dL (Mild hyperglycemia)	
 
Monitor fasting and preprandial glucose.
 
If persistent over 2 repeats over 3-4 weeks, consult Diabetologist and consider starting metformin
 

	Any blood glucose >250 mg/dL (Moderate to Severe hyperglycemia)	
 
Withhold GSK2820151 and instruct subject to notify investigator immediately. 
 
Monitor for ketoacidosis as clinically indicated.
 
If subject has evidence of ketoacidosis, initiate prompt therapy. Antihyperglycemic therapy with insulin is preferred. Consult Diabetologist/Endocrinologist . Careful monitoring should be performed to control for rebound hypoglycemia as effect of investigational product(s) resolve.
 
 
 
May consider restarting GSK2820151 at a reduced dose or dose level pre-event based on discussion with GSK Medical monitor.
 

Toxicity	Dose Adjustment/Stopping Criteria	Management Guidelines

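### Taken literally, the Appendix 3 liver monitoring rule for subjects with liver metastases and raised entry ALT does not meet its own stopping rule, and it can never apply from an entry ALT of 3.33xULN upward

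*Protocol*

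**What the plan says.** Protocol Appendix 3 (Section 14.3) has two tables for subjects with documented liver metastases or tumour infiltration and an entry ALT above 2.5 and up to 5xULN.

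The stopping table has an ALT-absolute row that requires two things together: ALT of at least 5xULN and "≥2x baseline value". Two further ALT-based stops begin lower, at 3xULN combined with 1.5 times baseline: one for a value "≥ 1.5x baseline value that persists for ≥4 weeks" and one for a value "≥ 1.5x baseline value that cannot be monitored for 4 weeks". Bilirubin, INR and symptom stops are separate.

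The increased-monitoring table starts at "ALT ≥ 3x ULN and 1.5x baseline value" and is capped by a less-than sign followed by "5x ULN and 2x baseline value". It also requires bilirubin below 2xULN, no liver or hypersensitivity symptoms, and a subject who can be monitored weekly for 4 weeks. When it applies, there are two actions: "Notify the GSK medical monitor" within 24 hours, and "Subject must return weekly for repeat liver chemistries" until values resolve, stabilise or return to within baseline, or a stop is met.

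The Liver row of Table 12 (Section 14.7.1) adds no rule of its own. It says "Refer to procedures outlined in" Appendix 3.

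**The concern.** A monitoring rule should cover every value at or above its lower trigger and below the stop. The stop joins its two conditions with *and*, so its complement needs *or*. The monitoring row uses *and* again. If that word means *both*, as it does in the row's lower trigger, the cap is 5xULN whatever the baseline, and a band of ALT values falls under neither rule.

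The result is also out of order. At an entry ALT of 3xULN, a value of 4.5 to <5xULN would trigger the notice and weekly tests, 5 to <6xULN would trigger neither, and 6xULN would stop treatment. The companion row for entry ALT up to 2.5xULN has no such break: it monitors from 3 to <5xULN and stops from 5xULN.

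At stake is how soon the sponsor hears of a rising ALT, and how soon a crossing of the stop is found, while dosing continues daily (Section 6.1) in a first-in-human study.

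**Working it through.** **Inputs.** Write b for entry ALT and A for on-study ALT, both in xULN, with b above 2.5. Table 4 admits ALT below 5xULN with liver metastases, while exclusion criterion 9 excludes only above 5xULN, so the examples stay below 5. The rules are those of Appendix 3. The test schedule is the liver chemistry row of Table 8.

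**Limits.**
- Lower trigger: max(3, 1.5b) = 1.5b, because 1.5 × 2.5 = 3.75 already exceeds 3.
- ALT-absolute stop: max(5, 2b) = 2b, because 2 × 2.5 = 5.
- Monitoring cap, literal: min(5, 2b) = 5.
- Literal monitoring range: 1.5b to <5. It is empty once 1.5b ≥ 5, that is b ≥ 3.33.
- Band under neither rule: max(5, 1.5b) to <2b.
- Uncovered share of the range 1.5b to <2b: (2b − max(5, 1.5b)) / 0.5b.

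| b | Monitored, literal | Under neither rule | Stop from | Uncovered share |
|---|---|---|---|---|
| 2.6 | 3.9 to <5 | 5 to <5.2 | 5.2 | 0.2/1.3 = 15% |
| 2.8 | 4.2 to <5 | 5 to <5.6 | 5.6 | 0.6/1.4 = 43% |
| 3.0 | 4.5 to <5 | 5 to <6 | 6 | 1.0/1.5 = 67% |
| 3.2 | 4.8 to <5 | 5 to <6.4 | 6.4 | 1.4/1.6 = 88% |
| 3.33 | none | 5 to <6.67 | 6.67 | 100% |
| 4.0 | none | 6 to <8 | 8 | 100% |
| 4.9 | none | 7.35 to <9.8 | 9.8 | 100% |

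The row is empty over (5 − 3.33)/(5 − 2.5) = 1.67/2.5 = 67% of the entry-ALT range named in its heading. These are shares of ALT ranges, not of patients. The documents give no distribution of entry ALT.

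**Who meets the band.** For b ≥ 3.33 the row cannot start, so any isolated, symptom-free value from 1.5b to <2b goes uncovered. For b < 3.33 a subject first seen between 1.5b and 5 has already started a monitoring event, and rising past 5xULN does not end it. The band then matters only when ALT passes over the monitored range between two tests.

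**Check of the repaired wording.** On a grid of b from 2.51 to 4.99 and A from 1 to 12, in steps of 0.01, 46,625 points lie at or above the lower trigger and below the ALT-absolute stop. The literal row covers 5,125 of them. The wording *A < 5xULN or A < 2b* covers all 46,625 and overlaps the stop at none.

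**Delay.** Table 8 places liver chemistry on Days 1, 6, 8, 13, 15, 22, 29, 43 and 57, then every 4 weeks (Day 85 next). The gaps are 5, 2, 5, 2, 7, 7, 14, 14 and 28 days. Through Day 29 the schedule is already at least weekly, so no testing is lost. After that, a crossing of 2b could be found up to 14 − 7 = 7 days later than under weekly tests in Weeks 5 to 9, and up to 28 − 7 = 21 days later after Week 9, with one dose per day. Visit windows are ignored.

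**The case against.** The strongest reply is that the literal reading is not the natural one. The step-down rule in the same table repeats the less-than sign before each of its limits; the disputed cap writes it once, ahead of the same 5x/2x pair that forms the stop. Read as *at or above the 3x/1.5x pair but below the 5x/2x pair*, the row is complete at every b. A reading that voids a rule over two thirds of its own range is suspect. This stands as a plausible account of what was meant. It does not settle the text, which nowhere says *not both*.

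Second, the persistence and cannot-monitor stops have no upper ALT limit, so they apply throughout the band and presuppose that the subject is being tested. If ALT stays at or above 1.5b for 4 weeks, treatment stops whether or not 2b was crossed. That bounds the exposure, but neither stop orders weekly tests or a 24-hour notice.

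Third, general safeguards remain: clinically significant laboratory results are recorded and followed (Section 8.3.9), adverse events are followed proactively and related ones notified promptly (Sections 9.2.2 and 9.2.3), the Safety Review Team reviews safety on an ongoing basis (Section 5.4.5), and a clinically significant Grade 3 toxicity in the first 4 weeks can count as a DLT (Table 3). None of these sets the two missing actions.

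Fourth, Section 5.4.1 sends sites to Figure 4 for this subgroup. The figure is not reproduced in the text available and may state the limit correctly.

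A reader might go further and infer that ALT in the band is unsupervised, or that the protocol as a whole has a hole. The safeguards just listed rule out the first, and the unseen figure prevents the second.

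**Conclusion.** The point holds as a wording defect of minor weight. On the literal reading, the monitoring row cannot be met for b of 3.33xULN or more, and an isolated, symptom-free ALT from 1.5b to <2b draws neither the ALT-absolute stop nor the monitoring actions. For lower b the gap is confined to ALT that skips the monitored range between tests, so the 15% to 88% shares should not be read as the chance that a subject goes unmonitored. What is lost is the 24-hour notice throughout and, after Week 5, weekly testing, with the 7-day and 21-day bounds above.

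This assumes that *and* in the cap means that both limits must hold, that bilirubin, INR and symptoms trigger nothing, that the subject can be monitored, and that Figure 4 does not say otherwise. On the alternative reading the gap is zero at every b.

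It would also be tempting to infer that subjects were harmed. The SAP (Section 1) reports 5 enrolled subjects, and nothing shows that any of them was in this subgroup.

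**What to change.** In the Appendix 3 monitoring row for this subgroup, replace the upper limit with: *but not both ALT ≥5xULN and ≥2x baseline* (equivalently, ALT <5xULN or <2x baseline). Check that Figure 4 shows the same limit, and correct it if it does not. No threshold changes.

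The cost is a few words in one appendix and a check of one figure. If sites had been applying the literal reading, the change adds a few medical monitor notices and, mainly after Week 5, a few weekly liver tests in a small subgroup.

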#### 14.4. Appendix 4: Liver Safety – Study Treatment Restart or Rechallenge Guidelines

Drug restart may be considered for a subject exhibiting compelling benefit for a critical medicine following drug-induced liver injury, if there is favorable benefit: risk ratio and no alternative medicine available.

If subject meets liver chemistry stopping criteria do not restart/rechallenge subject with study treatment unless:

- GSK Medical Governance approval **is granted** (as described below),
- Ethics and/or IRB approval is obtained, if required, and
- Separate consent for treatment restart/rechallenge is signed by the subject

If GSK Medical Governance approval to restart/rechallenge subject with study treatment **is not granted**, then subject must permanently discontinue study treatment and may continue in the study for protocol-specified follow up assessments

##### 1. *Rechallenge Following Liver Stopping Events that are Possibly Related to Study Treatment*

Following drug-induced liver injury, **drug rechallenge is associated with a 13% mortality across all drugs in prospective studies** [Andrade, 2009]. Clinical outcomes vary by drug, with nearly 50% fatality with halothane readministered within one month of initial injury. However, some drugs seldom result in recurrent liver injury or fatality.

Risk factors for a fatal drug rechallenge outcome include:

- Hypersensitivity [Andrade, 2009] with initial liver injury (e.g. fever, rash, eosinophilia)
- jaundice or bilirubin >2xULN with initial liver injury (direct bilirubin >35% of total)
- subject currently exhibits severe liver injury defined by: ALT  $\geq$ 3xULN, bilirubin  $\geq$ 2xULN (direct bilirubin >35% of total), or INR  $\geq$ 1.5
- serious adverse event or fatality has earlier been observed with drug rechallenges [Papay, 2009; Hunt, 2010]
- evidence of drug-related preclinical liability (e.g. reactive metabolites; mitochondrial impairment) [Hunt, 2010]

Rechallenge refers to resuming study treatment following drug induced liver injury (DILI). Because of the risks associated with rechallenge after DILI this should only be considered for a subject for whom there is compelling evidence of benefit from a critical or life-saving medicine, there is no alternative approved medicine available, and a benefit:risk assessment of rechallenge is considered to be favourable.

Approval by GSK for rechallenge with study treatment can be considered where:

- Investigator requests consideration of rechallenge with study treatment for a subject who is receiving compelling benefit with study treatment that exceeds risk, and no effective alternative therapy is available.
- Ethics Committee or Institutional Review Board approval for rechallenge with study treatment must be obtained, as required.
- If the rechallenge is approved by GSK Medical Governance in writing, the subject must be provided with a clear description of the possible benefits and risks of study treatment administration, including the possibility of recurrent, more severe liver injury or death.
- The subject must also provide signed informed consent specifically for the rechallenge with study treatment. Documentation of informed consent must be recorded in the study chart.
- Study treatment must be administered at the dose specified by GSK.
- Subjects approved by GSK Medical Governance for rechallenge with study treatment must return to the clinic twice a week for liver chemistry tests until stable liver chemistries have been demonstrated and then standard laboratory monitoring may resume as per protocol.
- If after study treatment rechallenge, subject meets protocol-defined liver chemistry stopping criteria, study treatment should be permanently discontinued.
- GSK Medical Monitor, and the Ethics Committee or Institutional Review Board as required, must be informed of the subject's outcome following study treatment rechallenge.
- GSK to be notified of any adverse events, as per Section 9.

## **2. Restart Following Transient Resolving Liver Stopping Events NOT Related to Study Treatment**

Restart refers to resuming study treatment following liver stopping events in which there is a clear underlying cause (other than DILI) of the liver event (e.g. biliary obstruction, pancreatic events, hypotension, acute viral hepatitis). Furthermore, there should be no evidence of alcoholic hepatitis or hypersensitivity, and the study treatment should not be associated with HLA markers of liver injury.

Approval by GSK for study treatment restart can be considered where:

- Investigator requests consideration for study treatment restart if liver chemistries have a clear underlying cause (e.g., biliary obstruction, hypotension and liver chemistries have improved to normal or are within 1.5 x baseline and ALT <3xULN).
- Restart risk factors (e.g., fever, rash, eosinophilia, or hypersensitivity, alcoholic hepatitis, possible study treatment-induced liver injury or study treatment has an HLA genetic marker associated with liver injury (e.g., lapatinib, abacavir, amoxicillin/clavulanate) are reviewed and excluded

- Ethics Committee or Institutional Review Board approval of study treatment restart must be obtained, as required.
- If restart of study treatment is approved by GSK Medical Governance in writing, the subject must be provided with a clear description of the possible benefits and risks of study treatment administration, including the possibility of recurrent, more severe liver injury or death.
- The subject must also provide signed informed consent specifically for the study treatment restart. Documentation of informed consent must be recorded in the study chart.
- Study treatment must be administered at the dose specified by GSK.
- Subjects approved by GSK Medical Governance for restarting study treatment must return to the clinic once a week for liver chemistry tests until stable liver chemistries have been demonstrated and then laboratory monitoring may resume as per protocol.
- If after study treatment re-start, subject meets protocol-defined liver chemistry stopping criteria, follow usual stopping criteria instructions.
- GSK Medical Monitor, and the Ethics Committee or Institutional Review Board as required, must be informed of the subject's outcome following study treatment restart.
- GSK to be notified of any adverse events, as per Section 9.

## 14.5. Appendix 5: Genetic Research

### Genetic Research Objectives and Analyses

The objectives of the genetic research are to investigate the relationship between genetic variants and response to medicine, including GSK2820151 or any concomitant medicines.

US Food and Drug Administration states that an *in vitro* companion diagnostic device (IVD) could be essential for the safe and effective use of a corresponding therapeutic product to:

- Identify patients who are most likely to benefit from a particular therapeutic product;
- Identify patients likely to be at increased risk for serious adverse reactions as a result of treatment with a particular therapeutic product;
- Monitor response to treatment for the purpose of adjusting treatment (e.g. schedule, dose, discontinuation) to achieve improved safety or effectiveness

Global regulatory requirements for IVD companion diagnostic tests are evolving. If a DNA-based IVD companion diagnostic device might be needed to identify patients who are appropriate for the GSK medicinal product(s) under investigation in this protocol, then GSK should collect and retain DNA samples from subjects who carry the genetic variant of interest as well as DNA samples from subjects who do not carry the genetic variants of interest to validate the performance of the companion diagnostic. Any IVD companion diagnostic research objectives should be described in subject informed consent forms.

Genetic data may be generated while the study is underway or following completion of the study. Genetic evaluations may include focused candidate gene approaches and/or examination of a large number of genetic variants throughout the genome (whole genome analyses). Genetic analyses will utilize data collected in the study and will be limited to understanding the objectives highlighted above. Analyses may be performed using data from multiple clinical studies to investigate these research objectives.

Appropriate descriptive and/or statistical analysis methods will be used. A detailed description of any planned analyses will be documented in the RAP prior to initiation of the analysis. Planned analyses and results of genetic investigations will be reported either as part of the clinical RAP and study report, or in a separate genetics RAP and report, as appropriate.

### Study Population

Any subject who is enrolled in the study can participate in genetic research. Any subject who has received an allogeneic bone marrow transplant must be excluded from the genetic research.

## Study Assessments and Procedures

A key component of successful genetic research is the collection of samples during clinical studies. Collection of samples, even when no *a priori* hypothesis has been identified, may enable future genetic analyses to be conducted to help understand variability in disease and medicine response.

- A 6 ml blood sample will be taken for Deoxyribonucleic acid (DNA) extraction. A Blood sample is collected at the baseline visit, after the subject has been randomized and provided informed consent for genetic research. Instructions for collection and shipping of the genetic sample are described in the laboratory manual. The DNA from the blood sample may undergo quality control analyses to confirm the integrity of the sample. If there are concerns regarding the quality of the sample, then the sample may be destroyed. The blood sample is taken on a single occasion unless a duplicate sample is required due to an inability to utilize the original sample.

The genetic sample is labelled (or “coded”) with the same study specific number used to label other samples and data in the study. This number can be traced or linked back to the subject by the investigator or site staff. Coded samples do not carry personal identifiers (such as name or social security number).

Samples will be stored securely and may be kept for up to 15 years after the last subject completes the study, or GSK may destroy the samples sooner. GSK or those working with GSK (for example, other researchers) will only use samples collected from the study for the purpose stated in this protocol and in the informed consent form. Samples may be used as part of the development of a companion diagnostic to support the GSK medicinal product.

Subjects can request their sample to be destroyed at any time.

